12.2 Disease Parameters

Measurable disease: Bi-dimensionally measurable lesions with clearly defined margins by MRI scan. All tumor measurements must be recorded in millimeters (or decimal fractions of centimeters).

Non-measurable disease: Uni-dimensionally measurable lesions or lesions with margins not clearly defined such as areas of T2/FLAIR signal abnormality or poorly defined enhancing abnormality.

Note: For cystic lesions, the only measurable part is any enhancement area around the cyst that is clearly defined and bi-dimensionally measurable. The cyst itself should not be considered measurable or non-measurable disease.

Target lesions: All measurable lesions that are residual of the lesion treated with MLA or that are located within the 3 cm radius of the rim of the MLA-treated recurrent tumor should be identified as target lesions and recorded and measured. Target lesions should be selected on the basis of their size (lesions with the longest diameter), but in addition should be those that lend themselves to reproducible repeated measurements. It may be the case that, on occasion, the largest lesion does not lend itself to reproducible measurement in which circumstance the next largest lesion, which can be measured reproducibly should be selected. When there are too many measurable lesions, choose the largest 3 lesions as target lesions to follow. The other measurable lesions should be considered evaluable for

the purpose of objective status determination.

Non-target lesions: All non-measurable lesions should be identified as non-target lesions and should also be recorded at baseline. Measurements of these lesions are not required, but the presence, absence, or in rare cases unequivocal progression of each should be noted throughout follow-up.

12.3 Methods for Evaluation of Measurable Disease

All measurements should be taken and recorded in metric notation using a ruler. All baseline evaluations should be performed as closely as possible to the beginning of treatment and never more than 2 weeks before the beginning of the treatment.

Clinical lesions: Clinical lesions will only be considered measurable on brain MRI when they are ≥ 5 mm diameter as assessed using a ruler.

Histology: This technique can be used to differentiate between partial responses (PR) and complete responses (CR) in rare cases when biopsy or surgical resection of a measurable lesion is clinically indicated.

Perfusion/CBV: This advanced brain MRI technique can be used as an adjunct test to determine treatment response or disease status. However, it should not be used as the primary or sole method to determine response or disease status.

Brain FDG-PET coupled with head CT or brain MRI: This advanced metabolic imaging technique can be used as an adjunct test to determine response or disease status. However it should be used as the primary or sole method of determining response or disease status.

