3.2 Inclusion Criteria – Arm B

1. Recurrent pediatric brain tumors determined candidates for MLA as determined by the treating neurosurgeon.
2. Unequivocal evidence of tumor progression by MRI (see Section 12).
3. There must be an interval of at least 12 weeks from the completion of radiotherapy to study registration except if there is unequivocal evidence for tumor recurrence per RANO criteria (see Section 12). When the interval is less than 12 weeks from the completion of radiotherapy, the use of PET scan is allowed to differentiate between evidence of tumor recurrence and pseudoprogression.
4. Recurrent lesions with dimension and contour that are determined by the treating neurosurgeon to be appropriate for MLA.
5. Age 3 to \leq 21
6. Karnofsky/Lansky performance status \geq 60%, see Appendix 1.
7. Adequate cardiac function as determined by a shortening fraction \geq 27% or left ventricular ejection fraction \geq 50% by echocardiogram within the past 1 year prior to registration.
8. Prior anthracycline therapy does not exceed 200 mg/m² total cumulative dose.
9. Adequate bone marrow and hepatic function as defined below (must be within 7 days of MLA):
 - a. Absolute neutrophil count (ANC) \geq 1000/mcl (G-CSF is allowed)
 - b. Platelets \geq 100 K/cumm
 - c. Hemoglobin \geq 9 g/dL (pRBC transfusion +/- ESA are allowed)
 - d. ALT \leq 3 x ULN

- e. $AST \leq 3 \times ULN$
 - f. $ALP \leq 3 \times ULN$. If ALP is $> 3 \times ULN$, GGT must be checked and be $\leq 3 \times ULN$.
 - g. $Bilirubin \leq 2 \times ULN$
10. At the time of registration, patient must have recovered from the toxic effects of prior therapy to no more than grade 1 toxicity.
 11. At the time of registration, patient must be at least 4 weeks from other prior cytotoxic chemotherapy.
 12. Women of childbearing potential and men must agree to use adequate contraception (hormonal or barrier method of birth control, abstinence) prior to study entry and for the duration of study participation. Should a woman become pregnant or suspect she is pregnant while participating in this study, she must inform her treating physician immediately.
 13. Ability to understand and willingness to sign an IRB approved written informed consent document (or that of legally authorized representative, if applicable).

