12.0 MEASUREMENT OF EFFECT

12.1 Antitumor Effect – Solid Tumors

For the purposes of this study, patients should be re-evaluated for response every 12 weeks on Arm A and every 8 weeks on Arm B. The DCE/DSC-MRI scan obtained within approximately 3 days after MLA will be used as the baseline scan for determining response. The DCE/DSC-MRI scans obtained at pre-MLA, post-MLA, and prior to 6 weeks post-MLA will not be assessed for disease response.

Response and progression will be evaluated in this study using the updated response assessment criteria for high-grade gliomas: Response Assessment in Neuro-Oncology (RANO) working group guideline [JCO 28(11): 1963-1972, 2010].

Criteria for Determining First Progression Depending on Time From Initial Chemoradiotherapy

First Progression	Definition
Progressive disease < 12 weeks after completion of chemoradiotherapy	
Progression can only be defined using diagnostic imaging if there is new enhancement outside of the radiation field (beyond the high-dose region or 80% isodose line) or if there is unequivocal evidence of viable tumor on histopathologic sampling (eg, solid tumor areas [ie, > 70% tumor cell nuclei in areas], high or progressive increase in MIB-1 proliferation index compared with prior biopsy, or evidence for histologic progression or increased anaplasia in tumor). Note: Given the difficulty of differentiating true progression from pseudoprogression, clinical decline alone, in the absence of radiographic or histologic confirmation of progression, will not be sufficient for definition of progressive disease in the first 12 weeks after completion of concurrent chemoradiotherapy.

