Progressive disease ≥ 12 weeks after chemoradiotherapy completion	
 1. New contrast-enhancing lesion outside of radiation field on decreasing, stable, or increasing doses of corticosteroids. 2. Increase by ≥ 25% in the sum of the products of perpendicular diameters between the first postradiotherapy scan, or a subsequent scan with smaller tumor size, and the scan at 12 weeks or later on stable or increasing doses of corticosteroids. 3. Clinical deterioration not attributable to concurrent medication or comorbid conditions is sufficient to declare progression on current treatment but not for entry onto a clinical trial for recurrence. 4. For patients receiving antiangiogenic therapy, significant increase in T2/FLAIR nonenhancing lesion may also be considered progressive disease. The increased T2/FLAIR must have occurred with the patient on stable or increasing doses of corticosteroids compared with baseline scan or best response after initiation of therapy and not be a result of comorbid events (eg, effects of radiation therapy, demyelination, ischemic injury, infection, seizures, postoperative changes, or other treatment effects).

Criteria for Response Assessment Incorporating MRI and Clinical Factors (Adapted from JCO 2010)

Response	Criteria
Complete response	
 • Requires all of the following: complete disappearance of all enhancing measurable and nonmeasurable disease sustained for at least 4 weeks. • No new lesions; stable or improved nonenhancing (T2/FLAIR) lesions. • Patients must be off corticosteroids (or on physiologic replacement doses only) and stable or improved clinically. Note: Patients with nonmeasurable disease only cannot have a complete response; the best response possible is stable disease.

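### Section 12.3 calls FDG-PET an adjunct and then, apparently through a dropped "not", the primary or sole method, against the MRI and clinical criteria behind PFS

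*Combined protocol and SAP*

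**What the plan says.** Section 12.3 has two consecutive paragraphs on advanced imaging.

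- **Perfusion/CBV.** It is allowed as an adjunct, with the limit: "However, it should not be used as the primary or sole method to determine response or disease status".
- **FDG-PET.** The first sentence gives it the same role: "This advanced metabolic imaging technique can be used as an adjunct test to determine response or disease status". The second reads: "However it should be used as the primary or sole method of determining response or disease status".

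The rules that determine response and progression are in Section 12.1, which says: "Response and progression will be evaluated in this study using the updated response assessment criteria for high-grade gliomas". The table of response categories is headed "Criteria for Response Assessment Incorporating MRI and Clinical Factors". The reference scan is also an MRI: "The DCE/DSC-MRI scan obtained within approximately 3 days after MLA will be used as the baseline scan for determining response".

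PET appears in one other operative place, Arm B inclusion criterion 3 (Section 3.2). Where radiotherapy ended less than 12 weeks earlier, "the use of PET scan is allowed to differentiate between evidence of tumor recurrence and pseudoprogression". For that same window, the first-progression table in Section 12.1 says: "Progression can only be defined using diagnostic imaging if there is new enhancement outside of the radiation field". Its alternative is unequivocal viable tumor on histopathology. PET is not listed.

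**The concern.** An adjunct test cannot also be the sole method. A reader who takes the second FDG-PET sentence at face value could call progression on a positive PET with a stable MRI, or set aside an MRI progression because PET was negative. Either would change a progression date with no stated criterion behind it.

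That date matters. Section 2.1 makes PFS (with OS) the primary objective in Arm A and 6-month PFS the primary objective in Arm B, and Section 12.3.6 runs PFS to progression or death. Section 14.0 also uses 6-month PFS as the outcome against which the permeability score is tested. In Arm B, Section 5.8 ties the end of etoposide to documented and confirmed progression, so the same inconsistency touches that rule.

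Equivocal scans are foreseeable here. Section 1.3 describes new peritumoral enhancement after MLA that often lasts several weeks, and Section 1.9 lists separating progression from MLA effect among the study's aims. Those are the cases in which a clinician might order a PET scan and then look to Section 12.3 for its weight.

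**Working it through.** The plan states no figure on this point, so the check is mainly a comparison of text.

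**1. Within Section 12.3.** The Perfusion/CBV and FDG-PET paragraphs share a structure: adjunct role, then a limit opening with However. The first limit contains not; the second does not. The contrast signalled by However makes sense only if the second sentence restricts the first. A lost word is by far the likeliest explanation.

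**2. Against the rest of Section 12.**

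| Element | Where | Basis | PET criterion? |
|---|---|---|---|
| First progression | 12.1 | Enhancement, T2/FLAIR, corticosteroids, clinical decline, histology | No |
| Response categories | 12.1 | MRI, corticosteroids, clinical status; failure to return through death or decline counts as progression | No |
| Baseline for response | 12.1 | Post-MLA MRI | No |
| Same-technique note | 12.1, below the response table | Follow-up technique must match baseline | No baseline PET is planned |
| Measurable disease | 12.2 | Bi-dimensional on MRI | No |
| Target and non-target lesions | 12.3.1, 12.3.2 | Products of diameters; unequivocal change | No |
| RANO summary | 12.3.3 | Five criteria, any one sufficient for progression | No |

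A call based on PET alone would have no threshold and no planned baseline scan.

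**3. Against the schedule.** Neither calendar (10.1, 10.2) lists PET. Section 11.0 ties the Tumor Response Form to each MRI. Any PET would be unscheduled, so the documents give no way to count the patients affected.

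**4. Entry to Arm B.** Criterion 2 requires unequivocal MRI progression of every Arm B patient. Criterion 3 limits the under-12-week exception to unequivocal recurrence by RANO, and only then permits PET to help separate recurrence from pseudoprogression. What remains unclear is how a PET result is to be used beside the under-12-week row of Section 12.1, which does not mention it.

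**5. Scale.** Input: six patients per arm (Sections 5.1.1 and 5.1.2). Let k be the number of patients whose 6-month status changes in the same direction because PET displaced the Section 12.1 criteria. With all six evaluable and none censored before 6 months, the shift is k/6:

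- k = 0: 0/6 = 0 percentage points
- k = 1: 1/6 = 16.7 percentage points
- k = 2: 2/6 = 33.3 percentage points

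The values of k are assumptions. Changes in opposite directions would offset each other. The Arm B denominator could be below six, because Section 5.5 requires two doxorubicin doses for efficacy evaluability and the footnote to the Section 12.1 response table removes distant-only progression from the PFS assessment. With five patients, one change would be 1/5 = 20 points.

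**The case against.** The strongest reply is that the rest of the protocol largely neutralises the sentence. The sentence before it, the opening However and the parallel paragraph all point to the intended meaning. Progression is governed by RANO, any one listed criterion suffices for it, and none is PET. A negative PET therefore has no route in those tables to cancel a qualifying MRI increase, and a positive PET meets no progression criterion. The same-technique note points to MRI, scans before 6 weeks post-MLA are not assessed for response, and the principal investigator reviews all patient data (Section 13.0). All of this stands, and it limits the practical reach. It does not remove the contradiction: the sentence is current text in the assessment section, and it states the opposite of the evident rule.

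The effect size is also open to challenge. One sixth is the weight of any patient in an arm of six and says nothing particular about PET. The study is a pilot with no power calculation (Section 14.0) and no stated success threshold for 6-month PFS, so no decision rule would flip. That too stands.

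A reader might infer from criterion 3 that patients can enter Arm B on PET alone, so that a child with pseudoprogression could be enrolled and later counted as a 6-month PFS success. The documents do not support this. Criterion 2 separately requires unequivocal MRI progression, criterion 3 itself requires recurrence by RANO, and the PET clause is permissive and replaces neither.

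**Conclusion.** The FDG-PET sentence is wrong as written and should be corrected. It contradicts the sentence before it, the parallel Perfusion/CBV paragraph and the criteria of Sections 12.1 to 12.3.3. Read literally, it would let PET alone set the progression status behind the primary PFS and 6-month PFS objectives.

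The size is 16.7 percentage points on a six-patient 6-month proportion for each patient affected, assuming full evaluability and no early censoring. For zero to two patients changed in the same direction, the range is 0 to 33 points. Zero has to be included because PET is neither scheduled nor named in any criterion.

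A reader might go further and conclude that the protocol intends PET to decide progression, or that PFS rests on MRI alone and is therefore overturned. Neither follows. The surrounding text shows the opposite intent, and the criteria also use clinical deterioration, corticosteroid conditions, histology and death. The PET clause at entry is a separate point of clarity. Overall this is a minor to moderate wording correction.

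**What to change.** - **Section 12.3, FDG-PET.** Insert not after should in the second sentence, so that it carries the same limit as the Perfusion/CBV paragraph and agrees with Section 12.1. The cost is one word, with no added visits, scans or patients.
- **Tumor Response Form (optional).** Add a field recording whether a PET scan contributed to the response or progression call. The cost is one item per form, and it would make the number of affected patients known.
- **Section 3.2, Arm B criterion 3.** Reconcile the PET clause with criterion 2 and with the under-12-week row of the first-progression table in Section 12.1, and state what part PET plays beside them. Which way to reconcile them is for the investigators. The cost is one clause.

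Because Section 5.8 uses documented progression to end etoposide, the corrected wording should be checked for consistency there as well.

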12.3.1 Evaluation of Target Lesions

Complete Response (CR): Disappearance of all target lesions.

Partial Response (PR): $\geq 50\%$ decrease compared with baseline in the sum of products of perpendicular diameters of all target lesions sustained for at least 4 weeks.

Progressive Disease (PD): At least a 25% increase in the sum of products of perpendicular diameters of at least 1 target lesion, taking as reference the smallest sum of products of perpendicular diameters on study (this includes the baseline sum if that is the smallest on study).

Stable Disease (SD): Neither sufficient shrinkage to qualify for PR nor sufficient increase to qualify for PD, taking as reference the smallest sum of products of perpendicular diameters while on study.

12.3.2 Evaluation of Non-Target Lesions

Complete Response (CR): Disappearance of all non-target lesions.

Non-CR/Non-PD: Persistence of one or more non-target lesion(s).

Progressive Disease (PD): Appearance of one or more new lesions and/or unequivocal progression of existing non-target lesions on stable or increasing doses of corticosteroids compared with baseline scan or best response after initiation of therapy* not caused by comorbid events (e.g. radiation therapy, demyelination, ischemic injury, infection, seizures, postoperative changes, or other treatment effects). Unequivocal progression should not normally trump target lesion status. It must be representative of overall disease status change, not a single lesion increase.

Although a clear progression of “non-target” lesions only is exceptional, the opinion of the treating physician should prevail in such circumstances, and the progression status should be confirmed at a later time by the review panel (or Principal Investigator).

12.3.3 Evaluation of Best Overall Response

The best overall response is the best response recorded from the start of the treatment until disease progression/recurrence (taking as reference for progressive disease the smallest measurements recorded since the treatment started). The patient's best response assignment will depend on the achievement of both measurement and confirmation criteria.

Summary of the RANO Response Criteria (Adapted from JCO 2010)

Criterion	CR	PR	SD	PD
T1 gadolinium enhancing disease	None	≥ 50% ↓	< 50% ↓ but < 25% ↑	≥ 25% ↑*
T2/FLAIR	Stable or ↓	Stable or ↓	Stable or ↓	↑*
New lesion	None	None	None	Present*
Corticosteroids	None	Stable or ↓	Stable or ↓	NA†
Clinical status	Stable or ↑	Stable or ↑	Stable or ↑	↓*
Requirement for response	All	All	All	Any*

Abbreviations: RANO, Response Assessment in Neuro-Oncology; CR, complete response; PR, partial response; SD, stable disease; PD, progressive disease; FLAIR, fluid-attenuated inversion recovery; NA, not applicable.

* Progression occurs when this criterion is present.

† Increase in corticosteroids alone will not be taken into account in determining progression in the absence of persistent clinical deterioration.

12.3.4 Duration of Response

Duration of overall response: The duration of overall response is measured from the time measurement criteria are met for CR or PR (whichever is first recorded) until the first date that recurrent or progressive disease is objectively documented (taking as reference for progressive disease the smallest measurements recorded since the treatment started).

The duration of overall CR is measured from the time measurement criteria are first met for CR until the first date that progressive disease is objectively documented.

Duration of stable disease: Stable disease is measured from the start of the treatment until the criteria for progression are met, taking as reference the smallest measurements recorded since the treatment started, including the baseline measurements.

12.3.5 Neurological Exam and Performance Status

Patients will be graded using the Karnofsky Performance Status scale and their neurological function evaluated as improved, stable or deteriorated in addition to objective measurement of tumor size. These parameters will be used to determine the overall response assessment.

12.3.6 Progression-Free Survival

PFS is defined as the duration of time from start of treatment to time of progression or death, whichever occurs first.

13.0 DATA AND SAFETY MONITORING

In compliance with the Washington University Institutional Data and Safety Monitoring Plan, the Principal Investigator will provide a Data and Safety Monitoring (DSM) report to the Washington University Quality Assurance and Safety Monitoring Committee (QASMC) semi-annually beginning six months after accrual has opened (if at least five patients have been enrolled) or one year after accrual has opened (if fewer than five patients have been enrolled at the six-month mark).

The Principal Investigator will review all patient data at least every six months, and provide a semi-annual report to the QASMC. This report will include:

- HRPO protocol number, protocol title, Principal Investigator name, data coordinator name, regulatory coordinator name, and statistician
- Date of initial HRPO approval, date of most recent consent HRPO approval/revision, date of HRPO expiration, date of most recent QA audit, study status, and phase of study
- History of study including summary of substantive amendments; summary of accrual suspensions including start/stop dates and reason; and summary of protocol exceptions, error, or breach of confidentiality including start/stop dates and reason

- Study-wide target accrual and study-wide actual accrual
- Protocol activation date
- Average rate of accrual observed in year 1, year 2, and subsequent years
- Expected accrual end date and accrual by arm
- Objectives of protocol with supporting data and list the number of participants who have met each objective
- Measures of efficacy
- Early stopping rules with supporting data and list the number of participants who have met the early stopping rules
- Summary of toxicities separated by arm
- Abstract submissions/publications
- Summary of any recent literature that may affect the safety or ethics of the study

The study principal investigator and Research Patient Coordinator will monitor for serious toxicities on an ongoing basis. Once the principal investigator or Research Patient Coordinator becomes aware of an adverse event, the AE will be reported to the HRPO and QASMC according to institutional guidelines.

